#### **8.2.2 Secondary Objectives**

The secondary objectives are:

- To evaluate baseline demographic and clinical data (disease characteristics and treatment history) of pediatric melanoma patients receiving nivolumab monotherapy, ipilimumab monotherapy, or nivolumab in combination with ipilimumab to treat advanced (unresectable or metastatic) melanoma
- To assess exposure to nivolumab monotherapy, ipilimumab monotherapy, or nivolumab in combination with ipilimumab (dose, frequency, treatment duration or number of infusions administered)
- To evaluate changes in nivolumab monotherapy, ipilimumab monotherapy, or nivolumab in combination with ipilimumab treatment following a Grade 3 or 4 AE, including reasons for discontinuation of nivolumab monotherapy, ipilimumab monotherapy, or nivolumab in combination with ipilimumab (including toxicity) and treatment with any subsequent therapies

- To evaluate long-term outcomes for pediatric melanoma patients treated with nivolumab monotherapy, ipilimumab monotherapy, or nivolumab in combination with ipilimumab (with emphasis on growth and sexual maturation)

## **9 RESEARCH METHODS**

### **9.1 Study Design**

This is an observational, national, retrospective cohort study based on secondary use of data from a registry in pediatric patients (12 to < 18 and < 12 years of age) with advanced (unresectable or metastatic) melanoma and with melanoma with involvement of lymph nodes or metastatic disease who have undergone complete resection, treated with nivolumab monotherapy, ipilimumab monotherapy, or nivolumab in combination with ipilimumab. The patients will be identified in the DMTR in the Netherlands. The DMTR collects real-world clinical effectiveness, safety data and healthcare utilization data.To date, the DMTR includes 14 participating adult centers in the Netherlands, selected by the Netherlands Association of Medical Oncology based on their expertise in the systemic treatment of melanoma, their infrastructure, and to ensure geographic distribution. With the extension of melanoma treatments to pediatric patients, an additional center, the Princess Maxima Center (PMC), a pediatric oncology hospital, will participate in the DMTR.

Because the treatment of all pediatric cancer patients is to be based at the PMC, the data for the current study will be primarily derived from this center. In the event a patient is seen at a participating DMTR center during adulthood, linked data will be provided when possible.

#### **9.1.1 Primary Endpoint**

The primary endpoints will be the frequency of Grade 3 and 4 treatment-related AEs and their management and outcomes.

#### **9.1.2 Secondary Endpoints**

The secondary endpoints will be:

- Baseline demographic, comorbidities, disease characteristics, and treatment history
- Exposure to nivolumab monotherapy, ipilimumab monotherapy, or nivolumab in combination with ipilimumab (dose, frequency, treatment duration, number of infusions)
- Changes in ipilimumab or nivolumab treatment: dose interruptions/discontinuations (with reason) and subsequent therapies
- Long-term outcomes: overall survival (OS), time to progression, assessment of growth and sexual maturation, and progression free survival (PFS)

### **9.2 Setting**

In the Netherlands, all pediatric patients are treated at 1 hospital, PMC. Therefore, the data for this study will be collected from this institution. Data collection is planned for approximately 10 years to obtain long-term follow-up on all enrolled pediatric melanoma patients treated with nivolumab monotherapy, ipilimumab monotherapy, or nivolumab in combination with ipilimumab.

### **9.2.1 Study Population**

The study population will consist of pediatric patients with:

- newly diagnosed or previously treated, advanced (unresectable or metastatic) melanoma who are treated with nivolumab monotherapy, ipilimumab monotherapy, or nivolumab in combination with ipilimumab and enrolled in the DMTR
- melanoma with involvement of lymph nodes or metastatic disease who have undergone complete resection and who are treated with adjuvant nivolumab monotherapy and enrolled in the DMTR

The patients will be divided into 2 cohorts (Cohort 1: 12 to < 18 years old; Cohort 2: < 12 years old), for each treatment (nivolumab monotherapy, ipilimumab monotherapy, or nivolumab in combination with ipilimumab) to make a total of 6 sub-cohorts.

### **9.2.2 Inclusion Criteria**

- < 18 years of age at first dose of nivolumab monotherapy, ipilimumab monotherapy, or nivolumab in combination with ipilimumab (index date) used for the treatment of advanced (unresectable or metastatic) melanoma
- Histologically or cytological confirmation of advanced (unresectable or metastatic) melanoma diagnosis or melanoma (with involvement of lymph nodes or metastatic disease) who have undergone complete resection or patients treated with nivolumab monotherapy in adjuvant treatment

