### **9.3.2 Exposure/Independent Variables of Interest**

- Exposure to nivolumab monotherapy, ipilimumab monotherapy, or nivolumab in combination with ipilimumab used for advanced (unresectable or metastatic) melanoma or exposure to nivolumab monotherapy in adjuvant therapy for melanoma with involvement of lymph nodes or metastatic disease who have undergone complete resection
  - Dose
  - Frequency
  - Treatment duration
  - Number of infusions administered
- Subsequent therapy post- nivolumab monotherapy, ipilimumab monotherapy, or nivolumab in combination with ipilimumab (time to next treatment, type, duration)

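### Inclusion criterion 1 covers only drug given for advanced melanoma, so read literally it shuts out the adjuvant nivolumab patients whom Section 9.2.1 includes; criterion 2's wording is ambiguous for the same group

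*Protocol*

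**What the plan says.** Section 9.2.2 of the protocol has two inclusion criteria.

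- **Criterion 1** sets the age limit (under 18) at the first dose of any of the three regimens, labels that dose the index date, and qualifies the drug as "used for the treatment of advanced (unresectable or metastatic) melanoma". It mentions no other use.
- **Criterion 2** opens with "Histologically or cytological confirmation of advanced (unresectable or metastatic) melanoma diagnosis". It then adds resected melanoma with nodal or metastatic involvement, and ends with patients "who have undergone complete resection or patients treated with nivolumab monotherapy in adjuvant treatment".

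Section 9.2.1, repeated in Section 4.5, defines two populations. The first is advanced melanoma treated with any of the three regimens. The second is "melanoma with involvement of lymph nodes or metastatic disease who have undergone complete resection and who are treated with adjuvant nivolumab monotherapy".

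Section 9.3.2 lists, next to exposure for advanced disease, "exposure to nivolumab monotherapy in adjuvant therapy for melanoma with involvement of lymph nodes or metastatic disease who have undergone complete resection". Section 7 lists adjuvant nivolumab among the agreed indication extensions, separately from the two advanced-melanoma uses of nivolumab.

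The first secondary objective (Section 8.2.2, also in Section 4.3 and the opening summary table) describes baseline data of patients who receive the drugs "to treat advanced (unresectable or metastatic) melanoma".

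**The concern.** Inclusion criteria are the rule by which patients are selected from the registry. Here the rule and the population it should deliver differ: one of the two populations in Section 9.2.1 has no route through criterion 1.

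The primary endpoint (Section 9.1.1) is the frequency of Grade 3 and 4 treatment-related adverse events. Section 9.7.1 reports it as frequencies, counts and percentages, so eligibility fixes the denominator. Adjuvant patients can fall only under nivolumab monotherapy, so the whole effect lands there. Section 9.2.1 splits the study into six sub-cohorts and Section 9.5 expects fewer than 10 exposed patients a year, so a few patients counted in or out would visibly change a percentage. The group at risk is also one that the post-authorization commitment in Section 7 was meant to cover.

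**Working it through.** No formula in the plan bears on this. The check sets the sections side by side and runs test patients through the two criteria, both of which must be met.

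**Inputs**

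| Source | What it requires or covers |
|---|---|
| 9.2.2, criterion 1 | Under 18 at first dose; drug given for advanced (unresectable or metastatic) disease |
| 9.2.2, criterion 2 | Confirmed advanced disease, or resected disease, or adjuvant nivolumab |
| 9.2.1, second population | Resected disease **and** adjuvant nivolumab |
| 9.3.2 | Adjuvant nivolumab is an exposure of interest, separate from advanced disease |
| 7 | Adjuvant nivolumab is a separate agreed indication |

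**Patient A: age 15, resected melanoma with nodal involvement only, adjuvant nivolumab.**
- Section 9.2.1: in the study.
- Criterion 1: not met. The disease is neither unresectable nor metastatic in the sense in which the protocol separates the two groups, and the drug is adjuvant.
- Criterion 2: met.
- Result: excluded, contrary to Section 9.2.1.

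**Patient B: as A, but with resected metastatic disease.**
- Section 9.2.1: in the study.
- Criterion 1: arguable. The word metastatic could be stretched to cover the patient, but Sections 7, 9.1, 9.2.1 and 9.3.2 all keep resected metastatic disease apart from advanced disease.
- Result: depends on the reader.

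**Patient C: as A, but without histology or cytology, with criterion 1 corrected to admit adjuvant use.**
- Criterion 2: if confirmation governs the whole list, not met. If the last 'or' opens a stand-alone alternative, met.
- Result: the sentence allows both readings, because confirmation of patients treated is not grammatical.

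**Linking word.** Section 9.2.1 says "who have undergone complete resection and who are treated with adjuvant nivolumab monotherapy and enrolled in the DMTR", whereas criterion 2 has "complete resection or patients treated with nivolumab monotherapy in adjuvant treatment". In 9.2.1 resection and adjuvant nivolumab are joint conditions; in criterion 2 they are alternatives.

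**Size.** There are 3 regimens × 2 age cohorts = 6 sub-cohorts. Adjuvant patients can occur only under nivolumab monotherapy, so 2 of the 6 are affected. Let *N* be the number of nivolumab monotherapy patients intended by Section 9.2.1, *a* the share of them treated in the adjuvant setting, and *n* the share of those adjuvant patients with nodal involvement only. Reading criterion 1 literally, the denominator falls from *N* to

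- *N*(1 − *a*) if all adjuvant patients fail, or
- *N*(1 − *a·n*) if resected metastatic patients are let through.

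The protocol gives neither *a* nor *n*. Each could lie anywhere between 0 and 1, so no figure follows.

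**The case against.** **Intent is plain.** Sections 4.5, 7, 9.1, 9.2.1 and 9.3.2 all name the resected or adjuvant group, and criterion 2 itself does so. The milestones (Section 4.10 and the footnote to Table 6-1) say that all pediatric registry patients who received any of the three regimens are included. That statement is about timing, but it carries no indication limit. A data manager would probably keep these patients. This stands as a reading of intent and makes the problem a drafting contradiction, not a chosen restriction. It does not remove the contradiction, because the operative criterion still says otherwise.

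**Some adjuvant patients may pass.** Resected metastatic disease could be argued to meet criterion 1. This narrows the claim; patients with nodal involvement only still fail.

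**Stronger readings of criterion 2.** A reader might infer that it waives histology for adjuvant patients, or admits resected patients on ipilimumab or the combination. Neither holds while criterion 1 is read literally, since those patients have already failed it. The waiver is only one parsing of an ungrammatical sentence, and no section expresses an intent to drop confirmation.

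**Secondary objective.** A reader might infer that baseline data would be lost for adjuvant patients. The baseline endpoint (9.1.2), covariates (9.3.3) and analysis (9.7.2) have no advanced-only limit, so the wording has little practical effect.

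**Shifting denominators.** A reader might also expect the rule to be applied differently from one annual abstraction to the next. Nothing in the protocol suggests that. Because data come retrospectively from charts, a registered patient who was wrongly left out could be recovered later.

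**Conclusion.** Criterion 1 is wrong as written. It conflicts with the second population in Section 9.2.1, with Section 9.3.2 and with the indication basis in Section 7. Read literally, it removes from the nivolumab monotherapy denominators at least the resected patients with nodal involvement only, and possibly every adjuvant patient. This rests on two premises: that inclusion criteria apply jointly, and that the protocol means what it repeatedly says in treating the resected group as distinct from advanced disease.

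The weakness in criterion 2 is ambiguity, secondary to the first point. It takes effect only when criterion 1 is repaired, so the two should be corrected together. The wording of the first secondary objective is a matter of consistency.

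The effect on the denominator cannot be quantified because the protocol gives no adjuvant share. The contradiction itself does not depend on that share.

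**What to change.** 1. **Criterion 1 (Section 9.2.2).** Cover both populations of Section 9.2.1: under 18 at the first dose of (a) any of the three regimens for advanced melanoma, or (b) adjuvant nivolumab monotherapy for completely resected melanoma with nodal or metastatic involvement.
2. **Criterion 2 (Section 9.2.2).** Require histology or cytology for the qualifying diagnosis in both groups: advanced melanoma for (a), and completely resected melanoma with nodal or metastatic involvement, treated with adjuvant nivolumab, for (b). This joins resection and adjuvant nivolumab as Section 9.2.1 does. Do not shorten it to confirmation of melanoma alone, which would drop the present requirement that the advanced diagnosis itself be confirmed.
3. **First secondary objective (Section 8.2.2, Section 4.3 and the opening summary table).** Add the adjuvant setting.

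The cost is a few words in these places. No new data are needed, since the protocol already plans to collect adjuvant exposure and baseline variables.

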### **9.2.3 Exclusion Criteria**

- Participation in a clinical trial within the past 4 weeks prior to first dose with nivolumab monotherapy, ipilimumab monotherapy, or nivolumab in combination with ipilimumab or concurrently

## **9.3 Variables**

### **9.3.1 Outcomes/Endpoint Variables**

Grade 3 and 4 treatment-related AEs will be collected according to the current Common Terminology Criteria for Adverse Events (CTCAE) version at the time of AE collection.

The DMTR provides detailed information on patient and tumor characteristics, diagnostics, treatment strategies, AEs, time to progression, and survival.

Variables include the following:

- Grade 3 and 4 treatment-related AEs, including:
  - blood disorders, such as leukopenia, thrombocytopenia, anemia
  - neuropathy
  - gastrointestinal, such as colitis, perforation
  - skin toxicity
  - uveitis

- endocrinopathy, such as adrenal insufficiency, pituitary insufficiency, thyroid insufficiency, diabetes mellitus
- hepatitis
- hypersensitivity
- nephritis and renal dysfunction
- pneumonitis
- myocarditis
- other
- Grade 3 to 4 treatment-related AEs onset date
- Grade 3 to 4 treatment-related AEs resolution date
- Grade 3 to 4 treatment-related AEs action taken with nivolumab monotherapy, ipilimumab monotherapy, or nivolumab in combination with ipilimumab treatment: dose interruption, discontinuation
- Grade 3 to 4 treatment-related AEs management: concomitant (interventional) medication or procedure
- Grade 3 to 4 treatment-related AEs outcome: resolved, resolved with sequelae, unresolved, death, unknown
- Parameters related to growth and sexual maturation (eg, height, weight, Tanner stage)
- Efficacy outcomes: time to progression, PFS, OS

### **9.3.2 Exposure/Independent Variables of Interest**

- Exposure to nivolumab monotherapy, ipilimumab monotherapy, or nivolumab in combination with ipilimumab used for advanced (unresectable or metastatic) melanoma or exposure to nivolumab monotherapy in adjuvant therapy for melanoma with involvement of lymph nodes or metastatic disease who have undergone complete resection
  - Dose
  - Frequency
  - Treatment duration
  - Number of infusions administered
- Subsequent therapy post- nivolumab monotherapy, ipilimumab monotherapy, or nivolumab in combination with ipilimumab (time to next treatment, type, duration)

### **9.3.3 Other Covariates/Control Variables**

The following baseline demographic, tumor, and treatment characteristics will be collected:

- Demographics such as:
  - Age
  - Gender
- Disease Characteristics:
  - Date of initial diagnosis and American Joint Committee on Cancer (AJCC) Stage

- Date of diagnosis and AJCC Stage, prior to first dose with nivolumab monotherapy, ipilimumab monotherapy, or nivolumab in combination with ipilimumab
- Breslow depth (mm)
- Melanoma type
- Tumor location
- Mutation type(s) (eg, *BRAF* and/or other mutation types)
- Serum lactate dehydrogenase level(s)
- Serum protein S100 level(s)
- Presence of brain metastases
- Presence of liver metastases
- Prior melanoma therapy(ies)
- Clinical Characteristics
  - Comorbid conditions/prognostic indicators
  - Karnofsky/Lansky
- Concomitant Medications (given 30 days prior to first dose and up to 100 days post last dose of nivolumab monotherapy, ipilimumab monotherapy, or nivolumab in combination with ipilimumab):
  - Medication name
  - Medication category
  - Start date
  - Stop date
  - Reason for Use a) comorbidity, b) nivolumab- and/or ipilimumab-treatment related AEs c) management for melanoma disease-related event, d) other

Baseline characteristics are defined as characteristics assessed before the date and time of the first dose of nivolumab monotherapy, ipilimumab monotherapy, or nivolumab in combination with ipilimumab treatment (index date).

Additional variables, similar to those provided for the adult registry and/or as applicable for pediatric patients may be provided for further descriptive analysis.

## 9.4 Data Sources

Data will be abstracted annually and retrospectively from medical charts (secondary use of data) from all pediatric melanoma patients enrolled in the DMTR. Trained data managers will coordinate and perform data collection in the melanoma centers. The Dutch Institute for Clinical Auditing will supervise data collection and management; oncologists will supervise the registration process and confirm all results at the patient level.

Data are entered into the DMTR electronic case report form (eCRF) for all patients receiving treatment at PMC. The evaluation of nivolumab- and ipilimumab-treated pediatric melanoma patients for this PASS will be carried out using data from the DMTR. Given the comprehensive

list of information that is already collected in the current DMTR eCRF, the likelihood that important data will be missed is small.

Additional data concerning outcomes related to growth and sexual maturation (eg, height, weight, Tanner stage) among nivolumab- or ipilimumab-treated pediatric patients that are not specified in the current DMTR data specifications will be abstracted via a pediatric-specific case report form (CRF) annex to the current eCRF. The special pediatric-specific CRF annex ([Annex 4](#)), was designed in collaboration with the participating pediatric oncologists and the DMTR scientific board.

The DMTR collects and analyzes Grade 3 and 4 treatment-related AEs (according to the current CTCAE version at the time of AE collection), data associated with the treatment of melanoma and clinical outcomes of all Dutch patients diagnosed with advanced (unresectable or metastatic) melanoma, or melanoma with involvement of lymph nodes or metastatic disease who have undergone complete resection. Grade 1 and 2 events are not captured by the DMTR. Death is recorded as a consequence of a Grade 3 or 4 toxicity, or as a reason for treatment discontinuation, rather than reporting as a Grade 5 event. Furthermore, the DMTR CRF includes queries for AE terms specific to the immune-mediated nature of the toxicity associated with immune-modulating therapies such as nivolumab and ipilimumab.

The DMTR uses a web-based environment for data entry and data management and employs a secure website to provide participating healthcare professionals. The Registry receives continuous benchmarked feedback with respect to the number of patients treated, treatment patterns, toxicity rates, and survival data on a weekly basis in relation to the national average and in relation to the results of other anonymized melanoma centers. All results are discussed at the quarterly meetings of the Medical Committee, in which all centers participate.

As described earlier, the data collected in the extension of the DMTR to pediatric patients will be primarily derived from the PMC. The PMC is currently the sole treatment center in the Netherlands for pediatric oncology. This centralized treatment center was created specifically for pediatric oncology patients in order to provide specialized care with expertise concentrated at this site. This hospital sees all pediatric oncology patients from the Netherlands and some from neighboring countries.

## 9.5 Study Size

Given the rarity of the population of pediatric patients with advanced (unresectable and metastatic) melanoma, and the difficulty that has been encountered recruiting pediatric patients into a clinical trial with nivolumab monotherapy, ipilimumab monotherapy, or nivolumab in combination with ipilimumab treatment, enrollment of pediatric patients into the Dutch registry is expected to be relatively low. Furthermore, with the introduction and expanded use of new classes of medications, such as the programmed death-1 /programmed death-ligand 1 inhibitors, the treatment of advanced (unresectable and metastatic) melanoma is anticipated to evolve and perhaps lead to even less use of ipilimumab monotherapy for this indication.

Based on the annual incidence of all pediatric cancer in the Netherlands, the DMTR estimated 10 new cases of pediatric melanoma are expected annually in the Netherlands. However, not all

melanoma cases will present with the disease histology or severity to warrant treatment, nor will nivolumab or ipilimumab be the treatment of choice for all treatment-eligible pediatric patients. Therefore, it is estimated that there will be fewer than 10 nivolumab- or ipilimumab-exposed pediatric patients enrolled in the DMTR annually.

Data collection is planned for approximately 10 years to obtain long-term follow-up on enrolled pediatric patients treated with nivolumab monotherapy, ipilimumab monotherapy, or nivolumab in combination with ipilimumab. The follow-up period for an individual patient may vary depending on the index date.

## **9.6 Data Management**

The DMTR provides pharmaceutical companies, such as Bristol-Myers Squibb Company (BMS), with aggregate information regarding the use and performance of their drugs in clinical practice. As the data received for this study are secondary and abstracted retrospectively from medical charts, data management activities will be the responsibility of the DMTR. The sponsor will obtain annual reports, and clarify any additional analysis needed.

## **9.7 Data Analysis**

The data provided for pediatric patients will be divided into 2 cohorts, based on age at time of first dose of nivolumab monotherapy, ipilimumab monotherapy, or nivolumab in combination with ipilimumab treatment (index date). Cohort 1 will include patients 12 to under 18 years old at time of enrollment, and Cohort 2 will include patients < 12 years of age at the time of enrollment. Patients that were treated before the nivolumab or ipilimumab marketing approval date will be included and assigned to the appropriate age-based cohort, regardless of timing with respect to date of approval. Interim data on pediatric patients treated with nivolumab monotherapy, ipilimumab monotherapy, or nivolumab in combination with ipilimumab will be reported by BMS to the Pharmacovigilance Risk Assessment Committee in the Periodic Safety Update Report (PSUR), in the interim study report, and in the final study report.

A description of patient and tumor characteristics for all pediatric patients receiving alternative therapies will be provided, for the overall treatment landscape for this patient population.

